| Composition, roles and responsibilities of the coordinating center, steering committee, endpoint adjudication committee, data management team and other individuals or groups overseeing the trial, if applicable [5d] | 
The members of the Gerodent PLUS-research project (ADV, EB, NH, LP, PP, FM and BJ) and RC will advise on study design, interpretation of the data, writing of the report and the decision to submit the report for publication.
 
A stakeholder group was formed. They will oversee the project and provide advice according to their expertise. Members of this group are:
 
 - Vlaams Instituut Mondgezondheid (Gezonde Mond) - Logo Limburg on behalf of all Flemish Logo's - Expertisecentrum Dementie Paradox - Vlaams Instituut Gezond Leven - VZW Zorg-Saam ZKJ - Woonzorggroep GVO - Vivel - ELZ Scheldekracht vzw - ELZ RITS - Logo Midden West-Vlaanderen - Zorgband Leie en Schelde |

Introduction

[6a] Background and rationale

People are living longer, therefore the population is aging. By 2061, the number of people older than 55 years in Belgium will increase by a third to 35.4% of the total population. The number of people older than 85 is expected to double (1). Thus, healthy ageing is more crucial than ever to avoid straining the health care system.

The World Health Organization (WHO) defines healthy ageing as “the process of developing and maintaining the functional ability that enables wellbeing in older age”. (2) Chan's study from 2023 provides a good summary of the impact of oral health on healthy aging (3). Poor oral hygiene causes caries and periodontitis, resulting in a high level of tooth loss in older generations. Older people are also more susceptible to xerostomia or oral cancer (4). The effects of poor oral health extend beyond the mouth and have an impact on overall health e.g. the risk of aspiratory pneumonia-related death (4). Poor oral health is also associated with cardiovascular disease and diabetes (5). Additionally, tooth loss, xerostomia and oral cancer can cause chewing and swallowing problems, which can lead to reduced nutritional uptake (6). Furthermore, the psychological impact of oral health should not be ignored. Poor oral health can lead to pain, feelings of shame and reduced social contact. All of these have an impact on the quality of life of older adults (7).

Despite the fact that oral health is an important part of overall health, oral diseases are the most prevalent condition worldwide (8). Chan's 2021 systematic review reports a median untreated caries prevalence of 46% in Europe in older adults aged 60 years or above (9). Research from 2016 reported poor oral health among frail elderly people in Belgium. There was a high treatment need, and oral health was distressing (10).

Most oral diseases are preventable by maintaining good daily oral hygiene and periodic professional care (11-13). However, dental attendance is low in older adults. Research in Belgium from the period 2019-2021 showed that only 34% of the population received preventive oral care and 26% of the population did not go to the dentist at all (14). Likewise, a recent oral health consumption analysis indicated that 41.7% of adults over 65 years in Flanders in the period 2020-2022 had no contact with the dentist at all and only 32.2% of them went for regular dental checkups. Once more, it was confirmed in our own interview studies with older people that the majority did not have a regular dental check-up. The main reasons for not seeking dental care are bad previous experiences, not knowing its importance, edentulousness, fear of the dentist, perceived costs and practical issues in reaching a dental office (15-17).

There is little research on the effect of oral screening campaigns for improving oral health in older people. Therefore, the aim of this study is to investigate the effect of a low-threshold contact with an oral health professional, including an oral health examination, on dental attendance of older people (65 years of age or older).

[6b] Explanation for choice of comparators

Our interview studies and a review of literature showed that older people are not aware of the importance of regular dental attendance and don't always have enough skills to schedule a dental visit and find a new dentist after retirement of their previous one. (16, 18)

The intervention group will be provided with tools to facilitate dental contact and will be informed about the importance of regular dental visits. Participants are given the opportunity to receive an oral examination. Afterwards, each participant will receive brochures with oral hygiene instructions to take home. Participants will receive information about any identified oral pathology. A referral letter for the dentist and a report for the general practitioner will also be prepared to increase social influence. If the participant doesn't have a dentist, the participant will receive a list of contact information for dentists in the area.

In the control group, no oral examination will be performed. However, participants will be given a list of nearby dentists and flyers with oral hygiene instructions.

In this way, we want to find out whether the presence of a dental professional with tailored advice is crucial to motivate an elderly person to good oral care.

[7] Objectives

The objective is to determine whether offering a low-threshold oral check-up to older adults, including oral health counselling, referral and report letters and a list of nearby dentists, results in a higher likelihood of contacting a dentist in the following 4 months compared to a control group that only received general oral health promotion leaflets and a list of nearby dentists.

Research hypothesis

We expect that elders who had a low-threshold oral check-up and received information about their oral situation will be more likely to contact a dentist.

[8] Trial design

This trial is designed as a randomized, controlled, non-blinded, superiority trial with two parallel groups. Randomization will be performed as block randomization with a 1:1 allocation. For practical reasons, each block will consist of 8 to 12 people.

Methods: Participants, interventions and outcomes

[9] Study setting

The study will be conducted within two specific regions in Flanders, Belgium. All service centers within the primary care zones RITS and Scheldekracht will be invited to participate in the study. Organizations focusing on older people will also be contacted to spread our call for participation in the study.

[10] Eligibility criteria

Older people are included when they meet the following criteria: they are 65 years of age or older, home-dwelling within the selected regions, they are Dutch speaking, and they did not have a dental check-up in the last 12 months. (19) By home-dwelling, we mean anyone who does not reside 24/7 in a residential care facility. If it concerns a couple, only one person can participate. Participants should have sufficient cognitive ability to answer the questions. If we ask the questions and find that the older person is unable to answer them adequately due to cognitive impairment, he or she will not be included in the study.

[11a] Interventions

After filling out the interview based questionnaire (see Appendix), the participants will be randomized between the control group and the intervention group. This will ensure that there are equal numbers of frail people in both groups.

The participants in the intervention group will receive an oral examination. Subsequently, information about any identified problem will be given. Lastly, participants will receive a referral letter for their dentist and a report for the general practitioner. If the participants don't have a regular dentist, they will also be given a list with contact information of dentists in the area.

Both the intervention and the control group will receive a flyer with oral hygiene instructions adapted to their needs and if necessary a list with contact information of dentist in the area. These flyers are evidence-based brochures compiled by the Flemish institute of oral health ("Gezonde Mond") on performing good oral hygiene.

[11b] Interventions - modifications

If an elderly person is randomized into the intervention group but refuses to have an oral examination, this will be noted.

If an elderly person in the control group asks for an oral examination because of a particular problem, the elderly person will be given the advice to contact a dentist.

[11c] Interventions – adherence

At the end of the initial contact, participants will be reminded that they will receive a phone call after 4 months. All participants will receive a pen with the logo of Gerodent PLUS as a gift.

[11d] Interventions – concomitant care

No concomitant care is prohibited to the participants. The intent of the study is to examine whether older people find access to regular care due to our intervention.

[12] Outcomes

Primary Outcome Measures

[figure not shown]
Participants will be contacted 4 months after the initial contact by telephone to ask if they contacted a dental professional since the first contact. We will make four attempts to contact them, two in the

morning and two in the afternoon. Contact information of partner or caregiver will also be included, in case the participant cannot be reached.

If the older person has contacted a dental professional within 4 months of our initial contact, then this is considered a success. Due to a shortage of dental professionals in Flanders, there is often a fairly long waiting period before a patient can get an appointment. In addition, many professionals have implemented a patient stop. So we want to give the elders enough time to find a dental professional. Differences in proportions will be reported.

[figure not shown]
| | Intervention group | Control group |
|---|--------------------|---------------|
| Contacted a dentist within 4 months | | |
| Not contacted a dentist within 4 months | | |

[13] Participant timeline

[14] Sample size

We expect to activate 30% of the participants in the intervention group; in the control group, we expect a maximum of 10%. To detect a mean difference of 20% with equal allocation to both groups would require 129 persons in total. To allow for 33% drop-out, 194 persons will be recruited.

[15] Recruitment

Service centers within the RITS and Scheldekracht primary care zones will be asked if they are willing to participate in the study. A date will be arranged with the interested centers when the study can take place in their facilities.

Organizations and other local initiatives will also be contacted to spread our call for participation in the study. Older people will be able to sign up at a participating service center to participate in the study.

Furthermore, home nursing and home care service organizations in the region have agreed to assist with participant recruitment.

Methods: Assignment of interventions

Allocation

[16a] Sequence generation

Participants will be randomly assigned to either control or intervention group with a 1:1 allocation. Randomization will be stratified by frailty. Random permuted blocks will be created using SAS v9.4 with variable sizes to avoid that the treatment allocation can be predicted. For practical reasons block size will vary between 8 and 12.

[16b] Allocation concealment mechanism and [16c] Implementation

A randomization list (prepared by RC) will be processed in REDCap by a HIRUZ staff member. Screeners will not have access to this list. Allocation concealment will be ensured as the REDCap-program will not release the randomization code until the questionnaire was completed.

[17] Blinding (masking)

This study is an open trial. The researchers at timepoint 1 are not blind to allocations. Participants in the control group will not be informed by the researchers that other participants might receive an oral examination. Participants in the intervention group will be told that due to an excess of time, they will also receive an oral examination. There is no procedure for unblinding needed.

At timepoint 2 the person will be contacted again by a different researcher than the researcher of the first contact, that way the researcher does not know in which group the participant was assigned.

Methods: Data collection, management and analysis

Data collection methods

[18a] Plans for assessment and collection of outcomes

The study will be piloted outside the region where the study takes place. Researchers PM and TC will be trained for screening of the oral status by researcher ADV. Interrater reliability will be calculated (20). Piloting will not be terminated until sufficient agreement is established.

No x-rays will be taken due to ethical concerns. Examiners will use a head lamp, a mouth mirror and periodontal probe for the oral examination. Denture plaque will be evaluated using methylene blue staining.

A script was integrated into the questionnaire on REDCap. It will not only display the questions, but will also display reminders so that no part of the survey can be forgotten (see Appendix). For example, researchers will have to check off that the informed consent form was signed or whether referral letters were completed and given to the participants. After each section of the questionnaire, the researcher will need to confirm that all questions in this section were completed.

Using REDCap, a calendar will be created automatically showing when the participants should be called for the questionnaire at timepoint 2.

[18b] Plans to promote participant retention and complete follow-up

- At the end of the initial contact, participants will be reminded that they will be called again 4 months later. Contact information for a partner, child or caregiver will also be noted. If a participant indicates they prefer to receive a letter, the home address will be noted.
- All participants will receive a pen with the logo of Gerodent PLUS as a gift.
- A 33% drop-out rate was taken into account when calculating the sample size.

- Refusal of the oral examination will be noted. However, since we are working from the intention to treat principle, the participant will remain in the intervention group.

[19] Data management

Data will be collected exclusively electronically through REDCap. REDCap is a secure web application for building and managing online surveys and databases. The type of activity that an individual user may undertake is regulated by the privileges associated with his/her account.

Once all data are collected, a copy of REDCap will be kept on the secure servers of Ghent University. Only members of the research team will have access to the data. If needed, data will be transferred using a Secure File Transfer platform, Belnet Filesender.

Statistical methods

[20a] Statistical methods for primary and secondary outcomes

Two weeks after the last telephone questionnaire was scheduled, we will end the data collection and the statistical analysis will be executed. The intervention group will be compared against the control group for having consulted a dentist within 4 months after the initial contact. Differences in proportions will be reported, logistic regression models will be used.

[20b] Methods for additional analyses (e.g. subgroup analyses)

[figure not shown]
Subgroup analyses will be purely exploratory:

- Impact of age on outcome
- Impact of gender on outcome
- Impact of education on outcome
- Impact of financial situation on outcome
- Impact of frailty on outcome.
- Impact of whether participant is dentate or edentulous on outcome.
- Impact of whether participant experienced oral problems the previous 6 months on outcome.

[20c] Methods in analysis to handle protocol non-adherence and any statistical methods to handle missing data

All randomized participants will be included in the “intention to treat”-analysis. This means that a participant allocated to the intervention group, who refuses an oral examination will remain in the intervention group.

If we cannot reach a participant at timepoint 2, the specified proxy will be contacted. If it appears that the participant has since died, they will be considered as drop-out. If it appears that the participant is not available (e.g., due to hospitalization), we will submit the questionnaire to the proxy. When we cannot reach an individual at all, we will address this missing data by applying multiple imputation per randomization arm. We will check for having natural teeth and when the last dental visit occurred, but this is not an exhaustive list.

Methods: monitoring

[21] Data monitoring

Since this study has no major safety concerns, no data monitoring committee will be composed. No interim analysis will be conducted.

[22] Harms

An adverse event refers to an unwanted side-effect during the study, which may or may not be causally related to the intervention or other aspects of participation in the study. We expect no such events to happen because of the design of the intervention. However, participants are informed that when an injury does occur, they may contact the investigator or a member of the research team. Contact information is included in the informed consent form.

[23] Auditing

There will be no auditing.

Ethics and dissemination

[24] Research ethics approval

This study was approved by an independent Medical Ethics Committee affiliated with Ghent University Hospital and Ghent University. The study is conducted according to the guidelines for good clinical practice (ICH/GCP) and the Declaration of Helsinki established to protect people participating in clinical studies. (Reference number ONZ-2023-0350). Written informed consent will be obtained from all the participants.

[25] Protocol amendments

Any modification to the protocol of the study will need a new approval by the Medical Ethics Committee, an amendment will be requested. The decision to amend the protocol will be discussed within the research team.

[26] Consent or assent

The informed consent forms [32] were approved by the Medical Ethics Committee affiliated with the Ghent University Hospital and Ghent University. The forms are addressed to the elderly person living at home. The participants should read the informed consent forms thoroughly and discuss them with the researcher. After all questions have been answered and upon agreement, the participant should sign the forms in the space provided.

The informed consent form requests the participant's permission to use his pseudonymized data for future scientific research in the same/similar research domain.

[27] Confidentiality

All the data will be collected pseudonymized. Each participant will be given a coded identification number. The key will be kept on a secured server of UGent to which only researchers of the Gerodent PLUS project will have access. The informed consent forms will be stored separately from study participants records identified by code number.

The informed consent form requests the participants permission to share the results of the oral examination with the family doctor or dentist. A referral and report letter will be given to the participant for these professionals.

Raw data will not be shared with members outside of the Gerodent PLUS-research team.

[28] Declaration of interests

The researchers declare that they have no competing interests.

[29] Access to data

Only members of the Gerodent PLUS-research team will have full access to the data. Raw data will not be shared with the sponsor or with journals.

[30] Ancillary and post-trial care

No disadvantages are expected for elderly people participating in this study; therefore no arrangements are made for ancillary care and post-trial care.

[31] Dissemination policy

Results of this study will be published and will be communicated to the Flemish Government. No professional writers will be used.

No later than 3 years after the collection of the final results, a description of the trial methods (including the protocol), deidentified data and all analyses will be shared upon request.

Appendices

[32] Informed consent materials

[33] Biological specimens

No biological specimens will be collected.

References

1. FOD Economie K, Middenstand en Energie. Statistieken over vergrijzing: portret van de bevolking van 55 jaar en ouder. 2017:54.
2. World Health A. Decade of healthy ageing: the global strategy and action plan on ageing and health 2016–2020: towards a world in which everyone can live a long and healthy life: report by the Director-General. Geneva: World Health Organization; 2020.

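### Eligibility looks only at past check-ups, so people with a dental visit already booked or treatment under way can be randomised; one baseline question would avoid the dilution they cause

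*Combined protocol and SAP*

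**What the plan says.** Section [10] of the combined protocol and SAP admits home-dwelling, Dutch-speaking people aged 65 or older in the two regions, with adequate cognition and one person per couple. Its only condition on dental use is "they did not have a dental check-up in the last 12 months". It does not define a check-up, and it does not mention future appointments or treatment under way. Section [11d] prohibits no concomitant care and gives the aim as learning whether older people reach regular care because of the intervention.

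Section [12] defines the endpoint: "If the older person has contacted a dental professional within 4 months of our initial contact, then this is considered a success". Section [20a] words it differently, comparing the arms "for having consulted a dentist within 4 months after the initial contact". Neither section says whether a visit arranged before enrolment counts. Section [12] also notes that "there is often a fairly long waiting period before a patient can get an appointment".

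Section [14] sizes the trial on the idea of activation: "We expect to activate 30% of the participants in the intervention group", with at most 10% in controls. Randomisation is stratified by frailty only (section [16a]). The exploratory subgroups in section [20b] contain no item on booked visits. Section [20c] names the date of the last dental visit, but only in connection with missing data.

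**The concern.** The trial asks whether a low-threshold check-up moves people to contact a dentist who otherwise would not. A person who already has a date in a dentist's diary, or is part-way through denture work, cannot be activated in that sense. The eligibility rule looks backwards only, so it does not screen such people out. The long waits reported in section [12] make existing bookings plausible in this population.

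Randomisation spreads these people evenly in expectation, so neither arm is favoured. It does not remove their effect on the size of the difference. They add participants whose result is much the same in both arms, so the contrast shrinks. Where they mostly succeed, both rates also move towards 50%, which raises the variance. Power for the activation question and the meaning of the reported difference in proportions are at stake.

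**Working it through.** **Inputs.** From section [14]: 30% against 10%, 129 analysed, 194 recruited. Not in the documents, so assumed: a two-sided 5% test, and the share f of participants already booked or in treatment (5%, 10% and 15% shown).

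**The plan's own figures.** The step to 194 reproduces: 129/(1 - 1/3) = 193.5, rounded up to 194. The 129 cannot be confirmed, because alpha, sidedness and power are not stated. With a two-sided 5% level and 80% power, the pooled formula gives 124, the unpooled 118 and the continuity-corrected 144. The unpooled formula with a one-sided 5% level and 90% power gives 128.5. I take 129/2 = 64.5, so 65 per arm. Exact enumeration of the chi-square test at 30% against 10% then gives power of 83.2%.

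**Dilution when these people come on top of the planned rates.** Let s be their chance of counting as a success, the same in both arms. Each arm's rate becomes p' = p(1 - f) + f·s. The f·s term cancels, so the difference is (30 - 10)(1 - f) = 20(1 - f) points: 19 at f = 5%, 18 at 10%, 17 at 15%.

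Example at f = 5%:
- All succeed: 0.30 × 0.95 + 0.05 = 33.5% and 0.10 × 0.95 + 0.05 = 14.5%.
- All fail: 0.30 × 0.95 = 28.5% and 0.10 × 0.95 = 9.5%.

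Exclusion without replacement keeps 30% against 10% with 65(1 - f) per arm, that is 62, 58 and 55.

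| f | Enrolled, all succeed | Enrolled, all fail | Excluded, not replaced |
|---|---|---|---|
| 5% | 33.5 v 14.5: 73.3% | 28.5 v 9.5: 80.6% | 62 per arm: 81.0% |
| 10% | 37 v 19: 64.2% | 27 v 9: 77.9% | 58 per arm: 79.7% |
| 15% | 40.5 v 23.5: 55.8% | 25.5 v 8.5: 74.9% | 55 per arm: 77.2% |

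If half succeed, power is 76.6% at f = 5% and 69.7% at f = 10%. In every row exclusion does at least slightly better, even with the smaller sample.

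**If the planned rates already include these people.** Planned power stays at 83.2%. Suppose f = 5% and all of them succeed. The rates among the rest are then (0.30 - 0.05)/0.95 = 26.3% and (0.10 - 0.05)/0.95 = 5.3%, a difference of 21.1 points. Excluding the 5% leaves 62 per arm and power of 92.3%.

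**If they are enrolled but stratified on.** At f = 5%, with 80% to 95% of booked people succeeding, a simulation put power at about 74% for the unadjusted comparison and 78% to 81% for an analysis stratified on booked status.

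**The case against.** A reader might infer that these people are near-certain successes and that the trial is therefore underpowered against its own plan. The documents do not support that, for four reasons.

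1. Section [12] asks about contact since the first contact. A booking made before baseline is not such a contact, so the visit itself would have to fall within 4 months. The long waits that make bookings plausible also make late visits plausible. If all of these people fail, exclusion gains only 81.0 - 80.6 = 0.4 points at f = 5% and 79.7 - 77.9 = 1.8 points at f = 10%.
2. Section [14] gives 10% as a maximum for controls. Adding f on top produces 14.5% or more, above that ceiling. Rates for enrolled participants are naturally read as including everyone enrolled. As rough context, section [6a] reports 41.7% of over-65s with no dental contact in 2020-2022 and 32.2% with regular check-ups, leaving 26.1%. Among those without regular check-ups, 26.1/67.8 = 38.5% had some contact in three years. At a constant rate that is 1 - (1 - 0.385)^(4/36), or about 5% per 4 months, which fits within the 10%.
3. No passage gives f. Some people in treatment will have had a recent check-up and so be excluded already. The questionnaire is in an appendix that is not part of the text available here, so it may already ask about bookings.
4. Broad eligibility is a legitimate choice for a trial about access to care, and randomisation keeps the comparison unbiased.

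All four stand, and they limit the point to an improvement. People on a waiting list also do not have a settled result: the referral letter or list of dentists could prompt contact elsewhere. What remains is that section [10] does not use booked status and the analysis text does not name it. The difference shrinks to 20(1 - f) points whether these people succeed or fail.

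**Conclusion.** The point holds as a cheap improvement to the design. People with a booked appointment or non-check-up treatment in progress are eligible, and their result is largely settled in either arm. They attenuate the difference in proportion to their share. At f = 5% the cost is between about 2.6 points of power (83.2 to 80.6, all fail) and about 10 points (83.2 to 73.3, all succeed), if they come on top of the planned rates. If the planned rates already include them, nothing is lost against plan, but about 9 points (83.2 to 92.3) could be gained by excluding them. These figures rest on an assumed f, an assumed two-sided 5% test, 65 analysed per arm, and the same success chance for these people in both arms. The documents support neither a claim of bias nor a claim that planned power is definitely lost.

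**What to change.** Before randomisation, within the existing REDCap questionnaire, ask whether a dental appointment is already booked or dental treatment is in progress. Add to section [10] that those who answer yes are not included. Do not exclude people who are only on a waiting list.

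If the sponsor prefers to keep eligibility broad:
- Record the same item and prespecify it as an adjustment or stratification factor in the primary analysis. If booked people all have the same result, ordinary logistic regression will separate on this item, so name a method that tolerates this, such as Mantel-Haenszel or Firth logistic regression.
- Report the difference in proportions among those not booked. Adjustment alone does not undo the dilution of the overall difference.

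Either way, state whether a visit arranged before enrolment counts as a success, and reconcile *contacted* in section [12] with *consulted* in section [20a].

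The cost is one added question, an amendment to eligibility or to the analysis text, and, with exclusion, a slightly smaller recruitment pool.

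### Do sections 6b, 7 and 11a give the two arms different rules for the list of dentists?

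*Combined protocol and SAP*

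**What the plan says.** Three sections of the combined protocol and SAP mention the list.

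- **Section 6b (choice of comparators).** For the intervention arm, when the person has no dentist, "the participant will receive a list of contact information for dentists in the area". For the control arm, after stating that no examination takes place: "However, participants will be given a list of nearby dentists and flyers with oral hygiene instructions". No condition is attached for controls.
- **Section 7 (objectives).** The intervention is described as a check-up "including oral health counselling, referral and report letters and a list of nearby dentists", "compared to a control group that only received general oral health promotion leaflets and a list of nearby dentists". Neither mention carries a condition.
- **Section 11a (interventions).** Intervention participants without a regular dentist are told that "they will also be given a list with contact information of dentists in the area". The next paragraph covers both arms: "Both the intervention and the control group will receive a flyer with oral hygiene instructions adapted to their needs and if necessary a list". On the flyers it adds: "These flyers are evidence-based brochures compiled by the Flemish institute of oral health".

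**The concern.** Read side by side, the sections do not match. Section 6b makes the list conditional in one arm and unconditional in the other, section 7 makes it unconditional in both, and section 11a makes it conditional in both.

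This seems to matter because the list bears on the behaviour that the trial measures. Section 6b names as a barrier that older people lack the skills to "find a new dentist after retirement of their previous one", and a list of nearby practices addresses that. Under a literal reading of 6b, a control who has a dentist receives the list and a comparable intervention participant does not. The contrast between arms would then be the check-up package minus a list for some people, not the check-up package alone. Section 6b also says that the trial is meant to show whether a dental professional's tailored advice is what motivates people, and that reading needs a shared background in both arms.

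A smaller oddity is that section 7 calls the control leaflets general, while 11a says the flyer is adapted to need in both arms.

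**Working it through.** No figure in the plan depends on the list rule, so the check is a comparison of texts. The entries show whether the list is given (intervention / control).

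| Section | No regular dentist | Has a regular dentist |
|---|---|---|
| 6b | yes / yes | no / yes |
| 7, read literally | yes / yes | yes / yes |
| 11a, if need means no regular dentist | yes / yes | no / no |

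1. **No regular dentist.** The three sections agree. The people for whom the list most plainly serves a purpose get it in both arms under every reading.

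2. **Has a regular dentist.** The entries differ, but they do not carry equal weight. Section 7 is one sentence naming the components of each condition. Leaving out a condition there is compression, and it uses the same short phrase for both arms. Section 6b explains why the comparator was chosen, and its control sentence may well use that phrase as shorthand too. Only 11a is written as a description of delivery.

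3. **What 11a implies.** One sentence with one qualifier covers both arms. The qualifier is not defined, but the paragraph before it supplies the natural meaning, namely no regular dentist. If it is meant more widely, for example to include someone whose dentist has retired, the last cell changes for some participants. It changes in both arms together, so the rule remains equal.

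4. **The group exists.** Eligibility in section 10 requires no check-up over the preceding 12 months, not the absence of a dentist, and 11a provides a referral letter addressed to the participant's own dentist. The second column is therefore not empty. Its size is not given.

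5. **Can an effect be calculated?** It cannot. That would need the share of participants with a regular dentist and the effect of a list on such people, and neither is stated. Section 14 gives the planned rates of 30% and at most 10% without saying which list rule they assume. Even the direction under 6b is open, since the people affected already have a dentist, while the barrier named in 6b is finding a new one.

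6. **The flyers.** Section 11a says they are ready-made institute brochures. Picking the brochure that suits a person fits both descriptions, so there is no contradiction.

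**The case for a change.** The best argument for a change is that a contradiction survives charitable reading. Suppose that section 7 merely omits the condition and that need in 11a means no regular dentist. Section 6b still gives the list to all controls where 11a does not, and 6b is the section that defines the comparator's purpose. In addition, section 17 says that staff at the first contact know the allocation, and sections 16b and 16c release it only once the questionnaire is complete. An undefined test of need could then be applied with the arm known. Section 12 notes that many practices no longer accept patients, so need is not always obvious. The repair would take a few words.

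The wording mismatch between 6b and 11a stands. The rest carries less weight. Whether someone has a regular dentist is a simple fact to establish, and 11a gives staff no ground for treating the arms differently. Section 18a describes a script built into the REDCap questionnaire, with reminders and check-offs, including for the referral letters. That script is a likely place for the list rule. The Appendix that holds it is not in the text available for this review, so the rule cannot be shown to be open in practice. A cheap edit is still no gain if it leaves the delivery, the analysis and the conclusion as they are.

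**Conclusion.** The concern does not call for a change. There is one literal mismatch, between the unconditional control sentence in 6b and the shared, need-based rule in 11a. It is confined to participants who already have a regular dentist, and it lies between a rationale and the section that governs delivery. Under 11a the arms are treated alike, and the primary comparison, the sample size and the intention-to-treat analysis are unaffected. Bringing 6b and 7 into line would be editorial tidying.

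This rests on two assumptions: that staff deliver the list as 11a describes, and that they apply the same test of need in both arms. If controls had in fact been given the list more widely, as 6b literally says, the arms would differ by more than the check-up package. The documents do not allow the direction or the size of the consequence to be worked out.
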